4.2 Inclusion Criteria

A subject must meet all of the following inclusion criteria to be eligible for participation in the study:

- 1. Is a male or female \geq 60 years of age
- 2. Can understand the nature of the trial and protocol requirements and provide written informed consent.

If the subject is deemed not competent to provide informed consent, the following requirements for consent must be met:

- a. The subject's legally acceptable representative (LAR) (or study partner/caregiver, if local regulations allow) must provide written informed consent
- b. The subject must provide written (if capable) informed assent
- 3. Subject requires some or complete assistance with one or more of the following:
 - a. Instrumental activities of daily living (communication, transportation, meal preparation, shopping, housework, managing medications, managing personal finances) OR
 - b. Basic activities of daily living (personal hygiene, dressing, eating, maintaining continence or transferring)
- 4. Meets clinical criteria for at least one of the following disorders, with or without cerebrovascular disease (CVD):
 - a. Parkinson's disease with or without dementia as defined by the Movement Disorder Society's Task Force (Appendix B)
 - b. Dementia with Lewy bodies (DLB) (Appendix C)
 - c. All-cause dementia, possible or probable Alzheimer's disease (AD) (Appendix A)
 - d. Frontotemporal degeneration spectrum disorders, including possible or probable:
 - i. Behavioral variant frontotemporal dementia (Appendix D)
 - ii. Progressive supranuclear palsy (Appendix E)
 - iii. Corticobasal degeneration (Appendix F)

Study: ACP-103-046 Clinical Study Protocol Amendment 7 Date: 5 March 2021

> e. Vascular dementia, including post-stroke dementia, multi-infarct dementia and/or subcortical ischemic vascular dementia (SIVD) (Appendix G)

- 5. Has an MMSE score ≥6 at Visit 1 (Screening) and Visit 2 (Baseline)
- 6. Has neuropsychiatric symptoms severe enough to warrant treatment with an antipsychotic agent, as evidenced by the Neuropsychiatric Inventory (NPI) score (Frequency×Severity) ≥4 on at least one of the following domains at Visit 1 (Screening) and Visit 2 (Baseline) (the domains at Screening and Baseline can be different):
 - a. Domain A Delusions; OR
 - b. Domain B Hallucinations: OR
 - c. Domain D Depression/Dysphoria; OR
 - d. Domain G Apathy/Indifference; OR
 - e. Domain H Disinhibition; OR
 - f. Domain I Irritability/Lability; OR
 - g. Domain K Sleep
- 7. Has a CGI-S score of ≥ 4 when assessing neuropsychiatric symptoms at Visit 1 (Screening) and Visit 2 (Baseline)
- 8. Has lived at the current place of residence for at least 3 weeks prior to Visit 1 (Screening) and there are no plans to move to a different location.
- 9. Has a designated study partner/caregiver who meets the following requirements:
 - a. In the Investigator's opinion, is in contact with the subject frequently enough to accurately report on the subject's symptoms and whether or not the subject is taking the study drug
 - b. In the Investigator's opinion, is considered reliable in providing support to the subject to help ensure compliance with study treatment, study visits, and protocol procedures
 - c. Is fluent in the local language in which study assessments will be administered
 - d. Agrees to participate in study assessments, has the capacity to provide informed consent, and provides written consent to participate in the study
- 10. Can come to the clinic for study visits with a study partner/caregiver
- 11. Has had a magnetic resonance imaging (MRI) or computed tomography (CT) scan of the brain within the last 3 years, and the scan or its final interpretation is available for review. If not available, a screening CT or MRI must be done during the screening period.
- 12. If the subject is taking a cholinesterase inhibitor, memantine, or both:

Final Version: 1.0

Study: ACP-103-046 Clinical Study Protocol Amendment 7

a. the dose of the medication(s) must be stable for at least 12 weeks prior to Visit 2 (Baseline) and there must be no current plan to change the dose; OR

- b. if the medication(s) was discontinued, the discontinuation must occur no fewer than 2 weeks prior to Visit 2 (Baseline).
- 13. If the subject is taking an antipsychotic medication at the time of screening, the antipsychotic medication must be discontinued 2 weeks or 5 half-lives (whichever is longer) prior to Visit 2. Investigators should not withdraw a subject's prohibited medication for the purpose of enrolling them into the study unless discontinuation of the medication is deemed to be clinically appropriate (e.g., symptoms are not well-controlled or the subject cannot tolerate the current medication).
- 14. If the subject is female, she must not be pregnant or breastfeeding. She must also be of non-childbearing potential (defined as either surgically sterilized or at least 1 year postmenopausal) or must agree to use a clinically acceptable method of contraception or be abstinent for at least 1 month prior to Visit 2 (Baseline), during the study, and 1 month following completion of the study.

Abstinence as a method of contraception is defined as refraining from heterosexual intercourse during the entire period of risk associated with the study treatments. This option is usually made for a specific moral, religious, legal, or health reason. If heterosexual intercourse does occur, an acceptable method of birth control is required.

Acceptable methods of birth control include the following:

- Condom, diaphragm, or cervical cap with spermicide
- Hormonal contraception, including oral, injectable, transdermal, or implantable methods
- Intrauterine device (IUD)

4.3 Exclusion Criteria

A subject must not meet any of the following exclusion criteria to be eligible for the study:

- 1. Is in hospice, is receiving end-of-life palliative care, or is bedridden
- 2. Has neuropsychiatric symptoms that are primarily attributable to current delirium or substance abuse (i.e., neuropsychiatric symptoms not related to neurodegenerative disease)
- 3. Has current evidence of an unstable neurological, cardiovascular, respiratory, gastrointestinal, renal, hepatic, hematologic, or other medical disorder, including cancer or malignancies that, in the judgment of the Investigator, would jeopardize the safe participation of the subject in the study or significantly interfere with the conduct or interpretation of the study
- 4. Has a history of epilepsy

Final Version: 1.0 Date: 5 March 2021

- 5. Has atrial fibrillation unless adequately anticoagulated
- 6. Has a history of myocardial infarction, unstable angina, acute coronary syndrome, or cerebrovascular accident within the last 6 months prior to Visit 1 (Screening)
- 7. Has any of the following:
 - a. greater than New York Heart Association (NYHA) Class 2 congestive heart failure (Appendix J)
 - b. Grade 2 or greater angina pectoris (by Canadian Cardiovascular Society Angina Grading Scale) (Appendix K)
 - c. sustained ventricular tachycardia
 - d. ventricular fibrillation
 - e. torsades de pointes
 - f. syncope due to an arrhythmia
 - g. an implantable cardiac defibrillator
- 8. Has a history of human immunodeficiency virus (HIV) or hepatitis C infection
- 9. Has a history of neuroleptic malignant syndrome or serotonin syndrome
- 10. Has a known personal or family history of long QT syndrome or family history of sudden cardiac death
- 11. Has any of the following ECG results at Visit 1 (Screening) or Visit 2 (Baseline):
 - a. If the subject is **not** on citalogram, escitalogram, or venlafaxine:
 - i. QTcF >450 ms, if QRS duration <120 ms
 - ii. QTcF >470 ms, if QRS duration ≥120 ms
 - b. If the subject is on citalogram, escitalogram, or venlafaxine:
 - i. QTcF >425 ms, if QRS duration <120 ms
 - ii. QTcF >450 ms, if QRS duration \geq 120 ms

At Screening, if the set of triplicate ECGs has a prolonged QTcF due to an identifiable cause, and it is medically appropriate to address that cause, a repeat set of triplicate ECGs may be performed during Screening at the discretion of the Medical Monitor.

- 12. Has a heart rate <50 beats per minute. If bradycardia is secondary to iatrogenic or treatable causes and these causes are treated, a heart rate assessment can be repeated during the screening period.
- 13. Has a clinically significant CNS abnormality that is most likely contributing to the dementia or findings on MRI or CT including:
 - a. intracranial mass lesion (including but not limited to meningioma [>1 cm³ with evidence of peritumoral edema] or glioma)
 - b. vascular malformation

- c. intracranial aneurysm >4 points by PHASES score (Appendix L)
- d. evidence of >4 hemosiderin deposits (definite microhemorrhage or superficial siderosis)
- 14. Has clinically significant neuroimaging or laboratory abnormalities during Screening that in the judgment of the Investigator would jeopardize the safe participation of the subject in the study. In consultation with the Medical Monitor, these subjects may be rescreened after appropriate treatment of their medical condition.
- 15. Has major surgery planned during the screening through end of the treatment or follow-up periods
- 16. Requires treatment with a medication or other substance that is prohibited by the protocol
- 17. Has a body mass index (BMI) $<18.5 \text{ kg/m}^2$ or known unintentional clinically significant weight loss (i.e., $\ge 7\%$) over past 6 months
- 18. The urine drug screen result at Visit 1 (Screening) indicates the presence of amphetamine/methamphetamine, barbiturates, cocaine, or phencyclidine (PCP). Subjects who test positive for amphetamines may be retested during Screening if they agree to abstain from the medication for the length of their participation in the study and if abstinence from medication usage is achieved at least 7 days prior to Visit 2 (Baseline). The repeat Screening test must be negative for them to participate in the study. The presence of benzodiazepines, marijuana (THC), or opiates does not necessarily exclude the subject from the study.
- 19. Is suicidal at Screening or Baseline as defined below:
 - a. If the subject can complete the Columbia Suicide Severity Rating Scale (C-SSRS), he or she must not be actively suicidal at Visit 1 (Screening) or Visit 2 (Baseline) (including, an answer of "yes" to C-SSRS questions 4 or 5 [current or over the last 6 months]) and must not have attempted suicide in the 2 years prior to Visit 1 (Screening); OR
 - b. If the subject is not able to reliably complete the C-SSRS in the Investigator's judgment, the subject must not be suicidal as assessed by the Global Clinician Assessment of Suicidality (GCAS) score (i.e., a score of 3 or 4) based on Investigator's assessment of behavior within the 3 months prior to Visit 1 (Screening) or since-last-visit at Visit 2 (Baseline); OR
 - c. The subject is actively suicidal in the Investigator's judgment

20. Has participated in or is participating in a clinical trial of any investigational drug, device, or intervention, within 30 days or 5 half-lives, whichever is longer, of Visit 2 (Baseline)

- 21. Has previously been enrolled in any prior clinical study with pimavanserin or is currently taking pimavanserin.
- 22. Has a significant sensitivity or allergic reaction to pimavanserin or its excipients
- 23. Is an employee or is a family member of an employee of Acadia Pharmaceuticals Inc.
- 24. Is judged by the Investigator or the Medical Monitor to be inappropriate for the study for any reason, including if the subject is judged to be a danger to self or others

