6.3.3 Height, Weight, and Body Mass Index

Height will be reported in centimeters.

Weight will be reported in kilograms.

Body mass index will be calculated using the following formula: Weight $(kg) / [height (m)]^2$.

6.3.4 **Electrocardiograms**

All 12-lead electrocardiograms (ECGs) will be complete, standardized recordings. Triplicate ECGs will be completed at Visit 1 (Screening) and a single recording will be completed at all other times. All ECGs will be centrally read; the interpretation by the central cardiologist is considered the official interpretation.

Study: ACP-103-046 Clinical Study Protocol Amendment 7

At Visit 1 (Screening) the mean QTcF/QRS values of all the tracings of adequate quality will be used to determine eligibility. If a site performs additional ECGs beyond the set of triplicate ECGs prescribed at Screening or the single ECG prescribed at Baseline, the mean QTcF/QRS values of all the tracings of adequate quality will be used to determine eligibility.

- At Screening, if the set of triplicate ECGs has a prolonged QTcF due to an identifiable cause, and it is medically appropriate to address that cause, a repeat set of triplicate ECGs may be performed during Screening at the discretion of the Medical Monitor
- At Baseline, a subject may be enrolled based on the machine read of the locally completed ECG. If the interpretation of the ECG by the central cardiologist indicates QTcF outside of the allowable range, the subject will be discontinued from the study, but this will not be considered a protocol deviation.

The subject must rest in a supine position before the ECG is obtained. ECG tracings (paper or electronic) will be reviewed and interpreted by a qualified clinician. ECG tracings and results (heart rate, RR, PR, QRS, QT, QTcF, and QTcB interval duration) will be included and summarized in the subject's study records.

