The results of the physical examinations at each visit will be tabulated by treatment group.

Electrocardiogram parameters at study visits will be summarized by treatment group. Change from Baseline values will also be summarized. Categorical analyses will be conducted on the incidence of subjects with prolonged QTc intervals and changes in QTc intervals in accordance with ICH guidelines.

9.5.5 **Interim Analyses**

One or more unblinded interim analyses of data from subjects who have exited the study (i.e., completed, enrolled into the open-label extension, or terminated early) may be conducted in order to support safety and efficacy evaluations for regulatory submissions.

9.6 **Data and Safety Monitoring Board**

An independent Data and Safety Monitoring Board (DSMB) will review interim safety data, including data on AEs and SAEs. The DSMB will be independent of the Sponsor and the Investigators and will be empowered to recommend stopping the study due to safety concerns. The DSMB may review blinded, unblinded or partially unblinded data, but the Sponsor and the Investigators will remain blinded to the data provided to the DSMB until the official unblinding of the database at the completion of the study. The membership, activities, responsibilities, and frequency of meetings will be described separately in the DSMB charter.

9.7 **Measures to Minimize Bias**

Eligible subjects will be randomized into one of two treatment groups (pimavanserin or placebo) in a 1:1 ratio using an interactive response technology (IRT) system. The randomization will be stratified by geographic region (North America, Europe, or rest of world). The assignments will be based on a pre-generated permuted-block randomization

schedule. Blinding will be assured by restricting access of Investigators and Sponsor personnel and/or designee to the treatment codes, and providing identical tablets and packaging for the pimavanserin and placebo treatments.

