14.3.7.1 ECG Variables

ECG variables include heart rate, PR interval, RR interval, QRS interval, QT interval, and QTc intervals. QTc intervals include QTcB (Bazett's formula) and QTcF (Fridericia's formula). QTcF will also be categorized into the following categories (msec):

• Observed: ≤ 450 , 451 to 480, 481 to 500, and ≥ 500

• Change from Baseline: ≤ 10 , 11 to 30, 31 to 60, and ≥ 60

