14.3.7.2 ECG Methods of Analysis

14.3.7.2.1 Observed Values and Change from Baseline

Observed values and the changes from Baseline of ECG variables will be summarized using descriptive statistics at Baseline and all scheduled post-Baseline visits. For the QTcF categorical analysis, the number and percentage of subject in each category will be summarized at each scheduled visit as well as overall post-Baseline maximum.

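### SAP 14.3.7.2.1 tabulates QTcF categories without reference to Baseline category, so the count above 450 ms mixes pre-existing with new prolongation and is not the incidence that Protocol 9.5.4 promises

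*Protocol*

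**What the plan says.** **Entry limits (Protocol 4.3, exclusion 11).** Subjects not taking citalopram, escitalopram or venlafaxine are excluded at "QTcF >450 ms, if QRS duration <120 ms" or at "QTcF >470 ms, if QRS duration ≥120 ms". For subjects on one of those drugs the limits are 425 ms (narrow QRS) and 450 ms (wide QRS). The limits apply at Screening and at Baseline.

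**Machine-read enrolment (Protocol 6.3.4).** "At Baseline, a subject may be enrolled based on the machine read of the locally completed ECG". The central reading follows. If it is out of range the subject is discontinued, but one who has taken a dose belongs to the Safety Analysis Set (SAP 4.2). ECG summaries use the central data (SAP 14.3.7).

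**What is promised (Protocol 9.5.4).** "Categorical analyses will be conducted on the incidence of subjects with prolonged QTc intervals and changes in QTc intervals in accordance with ICH guidelines".

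**What is planned (SAP 14.3.7).** Observed QTcF is grouped as up to 450, "451 to 480, 481 to 500" and a top category, whatever the QRS duration. For these categories "the number and percentage of subject in each category will be summarized at each scheduled visit as well as overall post-Baseline maximum". There are also change-from-Baseline categories, and Table 6 sets PCI limits of more than 500 ms and a change of more than 60 ms.

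**What is planned for other variables.** The SAP specifies shift tables for laboratory values (14.3.5.2), a split of laboratory PCI values by Baseline status (14.3.5.3) and a shift table for the cardiologist's interpretation (14.3.7.2.3). It specifies none for QTcF category.

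**The concern.** A wide-QRS subject who enters legitimately at 451 to 470 ms is in the first raised category before the first dose. If any post-Baseline ECG is still above 450 ms, that subject is counted there at the post-Baseline maximum, just like a subject who rose from 430 ms. The table cannot separate the two.

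This matters because QT prolongation is a risk that the protocol itself names, with an average of about 5 to 8 ms at 34 mg (Protocol 1.3.1). A mean shift of that size will seldom produce values above 500 ms or changes above 60 ms. Its categorical effect should show mainly as crossings of 450 ms, the one threshold at which the planned table is not an incidence. The change categories do not fill the gap, since a rise of 15 ms looks the same from 400 ms as from 445 ms.

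**Working it through.** **Plan's own figure.** The documents state no expected QTcF percentage, so there is none to reproduce. The sample-size figures concern the chance of at least one adverse event (1 − 0.99^375 = 0.977, as stated) and are not in question.

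**Step 1: which categories can hold an eligible subject at Baseline?**

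| Drug use | QRS | Highest QTcF admitted | Can start in 451 to 480 ms? |
|---|---|---|---|
| None of the three | <120 ms | 450 ms | No |
| None of the three | ≥120 ms | 470 ms | Yes, at 451 to 470 ms |
| One of the three | <120 ms | 425 ms | No |
| One of the three | ≥120 ms | 450 ms | No |

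No eligible subject can start at 481 ms or above. Machine-read enrolment may add a few subjects over these limits.

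**Step 2: what the table shows.** Let b be the share above 450 ms at Baseline, s the share of those with a post-Baseline maximum still above 450 ms, and i the new-onset incidence among subjects at or below 450 ms at Baseline.

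- Share shown above 450 ms: b·s + (1 − b)·i
- Excess over the incidence: b·(s − i)

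None of b, s and i is in the documents. I assume b of 1 to 4%, s of 0.7 to 0.9 and i of 3 to 6%.

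| b | s | i | Shown | Excess (points) | Pre-existing cases per 375 |
|---|---|---|---|---|---|
| 1% | 0.7 | 6% | 6.64% | 0.64 | 2.6 |
| 1% | 0.9 | 3% | 3.87% | 0.87 | 3.4 |
| 3% | 0.9 | 3% | 5.61% | 2.61 | 10.1 |
| 4% | 0.7 | 6% | 8.56% | 2.56 | 10.5 |
| 4% | 0.9 | 3% | 6.48% | 3.48 | 13.5 |

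The excess is therefore about 0.6 to 3.5 points per arm.

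**Step 3: effect on the comparison.** Take b = 3% and s = 0.9 in both arms, with i = 3% on placebo and 6% on pimavanserin. The table shows 5.61% and 8.52%. The difference is 2.91 points against 3.00 for new cases; the ratio is 1.52 against 2.00.

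**Step 4: where 1 to 4% comes from.** It comes from a simulation with these assumed inputs: 5 to 20% wide QRS before entry screening, QTcF means of 412 ms (narrow) and 442 ms (wide), between-subject SD 15 to 20, within-subject SD 10, drug effect 6.5 ms, two post-Baseline ECGs, 20% on the listed antidepressants, and an SD of 8 ms between machine and central readings.

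- About 1 to 4% of those enrolled are above 450 ms at Baseline, and they form about 18 to 37% of placebo subjects counted above 450 ms afterwards.
- Of those above 450 ms at Baseline, 73 to 77% on placebo and 88 to 90% on drug are above it again.
- At 12% wide QRS the planned table shows about 5.3 to 5.8% against 9.5 to 10.3% (ratio 1.8). New cases alone give 3.6 to 4.1% against 7.3 to 8.3% (ratio 2.0). The difference is about 4.2 to 4.5 points in the table and 3.7 to 4.2 for new cases.

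The ratio is diluted less here than in Step 3 because s is higher on drug.

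**The case against.** Several objections stand and limit the point.

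- **A reader might infer that the whole promised incidence has become a prevalence.** It has not. The highest entry limit is 470 ms, so the 481 to 500 ms and top categories and the 500 ms PCI limit are in effect incidences, apart from rare machine-read exceptions. The change categories and the 60 ms PCI limit refer to Baseline and deliver the second half of the protocol's promise.
- **A reader might infer that the treatment comparison is biased.** Randomisation makes the Baseline share equal in expectation, so the difference has no systematic bias. The ratio is diluted, but the SAP plans counts and percentages for ECG data, not ratios. With 375 per arm, 5.5% against 9.9% gives a ratio with a 95% interval of about 1.06 to 3.0, wide beside a shift of 0.2.
- **A reader might infer that a narrow-QRS user of a listed antidepressant, admitted only up to 425 ms, is invisible until QTcF rises by more than 25 ms.** That holds for the observed grid only; a rise of 11 to 25 ms falls in the 11 to 30 ms change category.
- **The Baseline row is informative.** Baseline is a scheduled ECG visit, so each arm's share above 450 ms should appear. With near-equal denominators, new cases lie between the post-Baseline share minus the Baseline share and the post-Baseline share itself. In the 12% scenario, with about 2.3 to 2.4% above 450 ms at Baseline, that is roughly 3 to 6% on placebo. These are bounds, not the incidence.
- **Table specifications are in a separate document (SAP 1).** A cross-tabulation may exist there. The SAP text does not require one, although it spells out shift tables elsewhere.
- **The SAP does not itself call 451 to 480 ms prolonged**, and the protocol defers to ICH guidelines that are not part of these documents. It is still the first category above the narrow-QRS entry limit, and the natural reading is that it counts.

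**Conclusion.** The point holds for the 450 ms threshold. There the planned table gives the share of subjects above the threshold after Baseline whether or not they were above it before, which is not the incidence in Protocol 9.5.4. The absolute percentages in both arms are too high as incidences and the ratio is pulled toward 1.

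That pre-existing cases can be counted follows from the text alone. How many there will be does not: the excess of roughly 0.6 to 3.5 points per arm rests on the assumed 1 to 4% above 450 ms at Baseline, on persistence of 0.7 to 0.9 and on new-onset incidence of 3 to 6%. The documents cannot show that the true figure lies in that range.

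This is a reporting gap. It does not touch sample size, conduct or the entry criteria, and exclusion 11 is not in error.

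**What to change.** In SAP 14.3.7.2.1:

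1. Keep the planned category table.
2. Add a QTcF shift table from Baseline category to maximum post-Baseline category, by treatment group. The denominator can follow the SAP's existing shift-table rule: subjects with a Baseline value and at least one post-Baseline value.
3. Report the number and percentage with any post-Baseline QTcF above 450 ms among subjects at or below 450 ms at Baseline.
4. Optionally, repeat item 3 by Baseline QRS (<120 ms, ≥120 ms), the split that exclusion 11 already uses.

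If the separate table specifications already contain such a shift table, it is enough for the SAP to say so. The cost is one or two extra tables from data already collected.
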